3.1 Analysis of primary and secondary outcomes

The primary analyses are designed as intention-to-treat and will be conducted using Stata version 16. Maternal and child outcomes are listed in Table 1. ***For all outcomes, the 36-month time point is considered primary.*** The primary child outcome is the Total Difficulties score from the Strengths and Difficulties Questionnaire (SDQ-TD). The primary maternal outcome is the Patient Health Questionnaire (PHQ-9). The secondary outcomes are detailed in Table 1. Of note, the Bayley scores (secondary outcome) will be scaled using the provided U.S. normed scales.

Separate outcome analysis will be conducted for mothers and for children. In both cases, data from perinataly depressed (by intervention arm) and perinataly non-depressed participants will be analysed jointly using linear mixed effects models so that all comparisons of interest can be estimated from the same model. The **identity link** will be used for **continuous outcomes** in order to estimate differences in mean outcomes.

Since our main predictor of interest is the treatment arm indicator (with non-depressed as a separate “arm”), which is related to the sampling variable, the primary analyses will be unweighted, and we will use restricted maximum likelihood (REML). If the model fails to converge after 50 iterations, then we use maximum likelihood. In addition, the between-within method will be used to apply small-sample corrections in the mixed effects framework.¹³ The reason for not using the sampling weights is that the sampling scheme is related to the main predictor of interest, so weighting should lead to minimal, if any, changes in the main results of interest. In addition, not using the sampling weights simplifies the modeling process and allows us to use estimation procedures (REML) shown to reduce bias, in addition to allowing us to use small-sample corrections on the models.

GEE analyses with a **log-link** and **Poisson distribution** will be used for **binary outcomes** in order to estimate prevalence ratios. The GEE analyses will apply the Kauermann-Carroll small-sample corrections with a t-test for inference.^{14,15} The GEE analyses will take into account clustering using an exchangeable working correlation matrix, and robust standard errors to account for potential model misspecification. All mixed models will include village cluster as a random intercept to account for the clustered study design. (Note that a separate random intercept for each group [intervention, control, non-depressed] was considered and formulated in section 3.1.1.1, but model convergence issues led us to revert to a single random intercept for cluster.) Additionally, clustering by peer group within the intervention arm will be potentially taken into account by adding an additional random intercept for each peer group.

Primary analyses of outcomes measured at a single follow-up time point are designed to include the following fixed factor variables: group (non-depressed, depressed intervention, depressed control), strata (11 Union councils), and any variables found to be imbalanced by loss to follow-up or at baseline (determined using $p < 0.10$). Under the assumption that those covariates explain the missing data mechanism, we will obtain valid estimates of the intervention effects using the complete case data (i.e. without the need for imputation or an alternative method).¹⁶ If there are concerns or evidence that covariates cannot explain the nature of the missingness (i.e. if the data are missing not at random), we will perform a series of sensitivity analyses based on the pattern mixture approach.¹⁷

Model assumptions will be assessed using examination of the residuals from the model and tests for linearity. In the presence of a ceiling or floor effect, we will also model the outcome using mixed effects tobit regression, which may allow us to more appropriately model the mean in such a situation.

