2.1 Principal research objectives and hypotheses to be addressed

The primary objective of the study is to evaluate the impact of a 36-month perinatal peer-delivered community-based perinatal depression intervention on (a) maternal depression and (b) child development. Our primary hypothesis for the perinatally depressed mothers is that the intervention will result in lower prevalence of depression at three years postnatal. Our primary hypothesis for the children is that the perinatal depression intervention will lead to improved developmental outcomes (see measures and constructs in Table 1) at three years of age. Additional child hypotheses address proposed mediators and moderators of the effects of the perinatal depression intervention on child outcomes; however, the mediators will be analyzed as part of a separate paper and so are not included in this document.

The second objective is to determine whether outcomes of perinatally depressed mothers and children in the intervention arm will converge to those in the reference group of perinatally non-depressed mothers and children as well as, secondarily, to determine whether there are any carryover effects of the intervention to benefit perinatally non-depressed mothers and children.

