2.4 Sample size calculation

Much of the following is copied or adapted from the THPP+ protocol paper.¹

The primary power calculations for the THPP+ study are for the c-RCT comparisons of perinatally depressed women and their children in the control vs. intervention arms at 36 months postnatally at the 5% two-tailed significance level. As with the THPP trial,² we assume 40 village clusters randomized in a 1:1 allocation ratio within 11 union councils with 14 perinatally depressed women per village cluster to yield a total sample size of 560 perinatally depressed women at baseline. In addition, for THPP+, we recruit 14 perinatally non-depressed women per village cluster for a total of 560 perinatally non-depressed women at baseline. We conservatively estimate that loss to follow-up (including infant mortality and maternal illness and death) of both perinatally depressed and perinatally non-depressed women at 36 months will be 20%. Therefore, the total sample size available at 36 months is anticipated to be 480 perinatally depressed and 480 perinatally non-depressed women and their children. Using standard formulae^{3,4} for a cluster randomized design and assuming intra-cluster correlation of 0.07 in the intervention arm and 0.05 in the control arm, the trial will have 90% power at 36 months to detect a difference in perinatally depression remission of 65% in perinatally depressed-Intervention vs. 45% in perinatally depressed-control for the anticipated total sample size of 480 perinatally depressed women at 36 months. For child outcomes, this sample size will yield power of more than 90% to detect a difference between arms in mean total difficulties (TD) score (range 0-40) of 3 points for children of perinatally depressed mothers using plausible estimates for intra-cluster correlations of 0.04-0.08⁵ and 5.2 for standard deviation for the TD score among 3 year olds.⁶

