Secondary comparisons mainly focus on child outcomes and are well powered. For the secondary hypothesis of equivalence between children of perinatally depressed mothers in the intervention arm and perinatally non-depressed mothers in the control arm, we will conclude equivalence if the 95% CI for the difference between the mean score in the two groups lies between -2 and 2 units. We note that differences of 1.0-2.0 points are often observed between boys and girls^{6,7}. With 220 children in each group and conservatively assuming an overall significance level of 2.5% (corresponding to the 95% CI), an SD of 5.2 and ICC of 0.04, and no difference between the groups, we will have 83% power to conclude equivalence.^{3,8} For the secondary research question of the community benefit (i.e. carryover) of the intervention for perinatally non-depressed women and their children, we will have 80% power to detect a 1.7 or greater impact of the intervention on mean TD score (Groups perinatally non-depressed-Intervention vs. perinatally non-depressed-Control, Figure 1) for the same assumptions of the primary comparison above.

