2.8 Data management

Baseline and follow-up outcome data is captured electronically using tablet computers. In addition, process data from peers is also collected. Baseline and outcome data is remotely uploaded as a CSV (comma-separated values) file to the main data server, which run on the software program ODK. Both files are compliant with good clinical practices (including a date and time stamp of original data entry and with an audit trail to document any subsequent changes). Process data is to be collected in paper form, and this is to be manually entered and stored as CSV files using the same data collection platform. THPP quality-related data is also be collected in paper form.

All data, range and consistency checks are performed at weekly intervals separately for each data source. Any queries identified are resolved promptly by the data management team, and the database is updated, maintaining the audit trail. Consistency checks are performed using PostgreSQL, pgAdminIII (ie SQL based queries run on the server). This includes Trial I.D duplication/mismatch, merging two tables in case any changes are made in the questionnaire.

Additional data quality checks are performed by a biostatistician at Duke University.

3 Data Analysis Plan

The main trial paper for both moms and children will focus on the 36-month outcomes solely. Statistical analysis will be conducted according to the CONSORT guidelines.^{11,12} A flow chart will show participation of both perinatally depressed (by intervention arm) and perinatally non-depressed

mothers and their children from recruitment in the third trimester through to 36 months postnatally (Figure 2 is an example, but in practice it will be more detailed). Withdrawals and loss to follow-up will be shown at 36-month post-intervention. All analyses will focus on comparison of three groups: perinataly depressed intervention, perinataly depressed control, and perinataly non-depressed, although we will test for a differential effect by non-depressed in intervention vs. control as a supplemental analysis.

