Baseline characteristics of recruited mothers will be reported by study arm for perinataly depressed women, and overall for perinataly non-depressed women. Continuous variables will be summarized by means and standard deviation (SD), or medians and the 25th and 75th percentile, if needed. Categorical variables will be summarized by counts and percentages. Distributions of outcomes will also be explored using graphical techniques such as box plots and histograms.

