3.1.1 Analysis models and code

For a continuous variable measured and/or analyzed at a single time point, we have the following model formulation (assuming no clustering at the peer group level and assuming one random intercept for cluster), which can easily be extended to the tobit framework:

$$Y_{jk} = \alpha_1 + \beta_1 X_{1jk} + \beta_2 X_{2jk} + \beta_3 U_k + \beta_5 C_{jk} + b_{0k} + \epsilon_{jk},$$

$$b_{0k} \sim N(0, \sigma_{b_{0k}}^2), \epsilon_{jk} \sim N(0, \sigma_{\epsilon_{jk}}^2)$$

for the j^{th} mother-child dyad in the k^{th} village cluster.

The fixed effects terms are as follows:

- Y_{jk} is the continuous outcome of interest
- X_{1jk} is a dummy variable for perinatally depressed intervention vs. control (1 if intervention; 0 if control) for mother j in cluster k
- X_{2jk} is a dummy variable for perinatal non-depressed vs. perinatally depressed control (1 if non-depressed; 0 if control) for mother j in cluster k
- U_k is the union council within which cluster k is located
- C_{jk} are other adjustors

The two random effects terms are as follows:

- b_{0k} is a random intercept for cluster k
- ϵ_{jk} is the residual measurement error for mother/child j in cluster k

This model can be fit with the following Stata code (with no additional adjustors):

```
mixed sdqTotal i.arm3 i.ucCode || clusterCode:, reml dfmethod(repeated)
```

Estimates of the pre-specified comparisons of interest will be derived from the fitted model.

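### Baseline PHQ-9 should be a fixed, stratum-centred covariate in the maternal PHQ-9 models; the SAP leaves its entry to a p<0.10 rule with unstated comparison groups and covariate form (low severity, nearly free to fix)

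*SAP*

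**What the plan says.** SAP section 3.1 lists the fixed effects of the primary single-time-point models: the three-level group, the 11 union councils, and "any variables found to be imbalanced by loss to follow-up or at baseline", decided at p<0.10. It names no candidate variables, no test and no comparison groups. The equation in section 3.1.1 has a generic term for further adjustors, and the code there has none. The sensitivity analyses in section 3.2 do not add baseline PHQ-9. Its only named use as a covariate is as a two-level severity moderator (section 3.3, Table 2).

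The comparison groups could be read in two ways. SAP section 3 states that "Baseline characteristics of recruited mothers will be reported by study arm for perinataly depressed women, and overall for perinataly non-depressed women", and that "All analyses will focus on comparison of three groups". Section 3.1 explains its choice of weighting with "Since our main predictor of interest is the treatment arm indicator (with non-depressed as a separate" arm. That suggests a three-group test. A test of the two randomised depressed arms is equally natural in a trial report.

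Baseline PHQ-9 is available for every woman. Protocol section 3.1 screens with it, and SAP section 2.2 defines the depressed as scoring 10 or more. The depressed and non-depressed groups therefore cannot overlap on it.

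**The concern.** The baseline value of an outcome is usually the first covariate to pre-specify. Here its inclusion depends on an undefined test, and each reading of the test has its own consequence. The two are alternatives and do not add up.

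- **Two-arm test.** Any imbalance between randomised arms is chance, so PHQ-9 mostly stays out and part of the precision it offers is lost.
- **Three-group test.** PHQ-9 is imbalanced by construction and always enters, so the precision is kept. But a raw common-slope term changes what the non-depressed coefficient means. It becomes the difference between groups at the same PHQ-9 score, where no data exist. The same happens if raw PHQ-9 enters as a predictor of loss to follow-up.

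The second reading touches the second objective, whether depressed "mothers and children in the intervention arm will converge to those in the reference group" of non-depressed women and their children (SAP section 2.1). For children, section 2.4 concludes equivalence if the 95% CI for "the difference between the mean score in the two groups lies between -2 and 2 units".

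**Working it through.** **1. The plan's own figure.** SAP section 2.4 says "the trial will have 90% power at 36 months to detect a difference in perinatally depression remission of 65"% against 45%, with 480 depressed women (12 per cluster, 20 clusters per arm) and ICCs of 0.07 and 0.05. The variance per cluster pair is (0.65×0.35 + 0.45×0.55)/12 + 0.07×0.65×0.35 + 0.05×0.45×0.55 = 0.0396 + 0.0283 = 0.0679. With 19 in place of 20 clusters (the usual small-sample correction), power = Φ(√(19×0.20²/0.0679) − 1.96) = 91.7%; with 18 it is 90.3%. The stated 90% reproduces. It applies to remission; no power is stated for mean PHQ-9.

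**2. Gain from always adjusting, mean PHQ-9.** The correlation r between baseline and 36 months within stratum is not in the documents, so 0.1, 0.3 and 0.5 are assumed. Selection at 10 or more and a three-year gap make low to middle values likelier. If variance falls at both levels, the SE ratio is √(1−r²). If it falls at the individual level only, the ratio is √{[ρ+((1−ρ)−r²)/m]/[ρ+(1−ρ)/m]}, with ρ = 0.05 to 0.07 and m = 11.2 to 12. Power from an illustrative 90% is Φ(3.242/ratio − 1.960).

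**3. Share lost under a two-arm test.** With c = 1.645, entry = 2(1−Φ(c)) = 10.0%. The share of the variance gain kept is entry + 2cφ(c) = 43.9%, so 56.1% is lost. If the test ignores clustering, c becomes 1.645/√(1+13×ICC): a baseline ICC of 0.05 gives 20.0% entry and 35.0% lost, and 0.07 gives 23.4% and 29.8%. If loss to follow-up selects PHQ-9 independently, the loss is 56%×0.9 = 50% at a 10% selection rate and 56%×0.5 = 28% at a 50% rate. So 56% is an upper bound.

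| Assumed r | SE fall, always adjusting | Power, always adjusting | Power points lost by the rule (56% case) |
|---|---|---|---|
| 0.1 | 0.3 to 0.5% | 90.2 to 90.3% | 0.1 to 0.2 |
| 0.3 | 2.6 to 4.6% | 91.4 to 92.5% | 0.8 to 1.4 |
| 0.5 | 7.3 to 13.4% | 93.8 to 96.3% | 2.1 to 3.3 |

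Example, r = 0.3 at both levels: the variance ratio is 0.91 when always adjusting and 1 − 0.439×0.09 = 0.960 under the rule, giving 92.5% and 91.1%.

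**4. Dichotomised PHQ-9.** Simulation with a log-link Poisson model (35% against 55% still depressed, 40 clusters of 12) gives SE falls of at most 0.1% at r = 0.1, 1.5 to 2.8% at 0.3 and 3.7 to 6.9% at 0.5. By the same formula the rule loses at most 0.03, 0.5 to 0.9, and 1.1 to 2.0 power points.

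**5. Three-group test with a raw linear term.** Raw PHQ-9 equals centred PHQ-9 plus a stratum mean, and the stratum mean is a function of the non-depressed dummy. So the raw coefficient for that dummy equals the centred one plus slope × gap, while the intervention coefficient is untouched. The baseline gap and SD are not in the documents; a gap of 8 to 12 points and an SD of 2.5 to 4 are assumed, so gap/SD runs from 8/4 = 2.0 to 12/2.5 = 4.8.

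- Shift in SDQ-TD points = r × (gap/SD) × 5.2, with the SD of 5.2 from section 2.4. At an assumed r of 0.05 between maternal PHQ-9 and SDQ-TD this is 0.5 to 1.2; at 0.10 it is 1.0 to 2.5.
- Generalised least squares for the three-group model (40 clusters, 11 strata, 12 per group per cluster, ICC 0.06) gives an SE for the non-depressed coefficient 1.27 to 2.13 times the centred one. A second run gave 1.30 to 2.21, so about 1.3 to 2.2. For intervention against control the ratio is 1.000.
- In simulation with a true non-depressed contrast of −3 and r = 0.1, the raw term gives −1.22 and the centred term −3.01. Type I error for the randomised comparison was 4.5 to 5.3% across r = 0.1 to 0.5 under every form of adjustment.

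**The case against.** Several points on the other side stand.

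- **The efficiency loss is small.** At r of 0.3 or less the rule costs at most about 1.4 power points, and less for the dichotomised outcome on which power was calculated.
- **Raw linear entry is only one possibility.** Section 3.1 describes the covariates as factor variables, and the SAP's only PHQ-9 grouping within the depressed is 10 to 14 against 15 or more. A 15-or-more indicator would also change the meaning of the contrast. On assumed truncated distributions and r of 0.05 to 0.10 it would do so by about 0.1 to 0.5 SDQ-TD points. The factor wording does not settle the form.
- **Raw and centred entry are the same fitted model.** Only the evaluation point differs. Section 3.1.1 says "Estimates of the pre-specified comparisons of interest will be derived from the fitted model", which leaves room for a contrast at stratum means but does not state one.
- **The margin belongs to a different contrast.** The ±2 limits in section 2.4 are for depressed-intervention against non-depressed control, whereas the model in 3.1.1 pools the non-depressed. Setting the shift beside the margin shows scale only.

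A reader might also infer that selecting covariates by p-value biases the treatment estimate, or that other imbalanced covariates should leave the primary model. The documents and the calculations support neither. Women are not randomised to being depressed or non-depressed, so imbalances across that line are not chance, and removing adjustment there is a separate question.

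**Conclusion.** The point holds as a low-severity, nearly free improvement. The SAP leaves open whether and how baseline PHQ-9 enters its primary models, and always adjusting is better at almost no cost.

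On the two-arm reading, the loss for mean PHQ-9 is about 0.1 to 0.2 power points at r = 0.1, 0.8 to 1.4 at 0.3 and 2 to 3 at 0.5. On the three-group reading nothing is lost in precision for the randomised comparison. The non-depressed contrasts, however, could be reported with an SE 1.3 to 2.2 times as large and a shift of about 0.5 to 2.5 SDQ-TD points. That requires both a raw linear term and contrasts read straight from the coefficients.

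All of these sizes rest on an assumed r, gap and baseline SD, and the power figures on a starting value that the SAP states for remission only. One might conclude that the randomised result is compromised, that the stated power is wrong, or that the child equivalence finding will be reversed. None of these follows: the randomised estimate is unbiased, the 90% reproduces, and the shift depends on a coding choice that the SAP does not make.

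**What to change.** Add to SAP section 3.1:

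1. The maternal PHQ-9 models, mean and dichotomised, always include baseline PHQ-9 centred within depression stratum, with one centre for both depressed arms, whatever the p<0.10 test shows.
2. Wherever baseline PHQ-9 enters a three-group model, including child models and entry as a predictor of loss to follow-up, it takes that centred form, and contrasts with the non-depressed are evaluated at each stratum's own mean.

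Leave the rule for all other covariates as it is. The cost is a few sentences and one extra parameter. No new data are needed, and the intervention estimate and its SE are the same as with raw adjustment.

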3.1.1 Analysis models and code

For a continuous variable measured and/or analyzed at a single time point, we have the following model formulation (assuming no clustering at the peer group level and assuming one random intercept for cluster), which can easily be extended to the tobit framework:

$$Y_{jk} = \alpha_1 + \beta_1 X_{1jk} + \beta_2 X_{2jk} + \beta_3 U_k + \beta_5 C_{jk} + b_{0k} + \epsilon_{jk},$$

$$b_{0k} \sim N(0, \sigma_{b_{0k}}^2), \epsilon_{jk} \sim N(0, \sigma_{\epsilon_{jk}}^2)$$

for the j^{th} mother-child dyad in the k^{th} village cluster.

The fixed effects terms are as follows:

- Y_{jk} is the continuous outcome of interest
- X_{1jk} is a dummy variable for perinatally depressed intervention vs. control (1 if intervention; 0 if control) for mother j in cluster k
- X_{2jk} is a dummy variable for perinatal non-depressed vs. perinatally depressed control (1 if non-depressed; 0 if control) for mother j in cluster k
- U_k is the union council within which cluster k is located
- C_{jk} are other adjustors

The two random effects terms are as follows:

- b_{0k} is a random intercept for cluster k
- ϵ_{jk} is the residual measurement error for mother/child j in cluster k

This model can be fit with the following Stata code (with no additional adjustors):

```
mixed sdqTotal i.arm3 i.ucCode || clusterCode:, reml dfmethod(repeated)
```

Estimates of the pre-specified comparisons of interest will be derived from the fitted model.

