The sampling unit within each cluster is the mother-child dyad. Women in the last trimester of pregnancy residing in one of the 40 study clusters will be identified through community surveillance normally conducted by community health workers (CHW). CHWs are utilized in most lower/middle income countries to deliver basic maternal and child health services. In Pakistan, each CHW covers 100 households and is informed of every pregnancy. Our research team has a long-standing relationship with the CHWs in the study areas. The CHWs will liaise with the research field staff which will seek informed consent from the pregnant woman and screen her for depression using the PHQ-9. We will offer enrollment to each woman who screens positive for depression and the first woman who subsequently screens negative. As a result, every cluster in the intervention and control arms will include women who score above and below the depression screening cutoff. Due to the community nature of the intervention, we anticipate that non-depressed women in the intervention clusters will benefit from the trial. Women who are suicidal, psychotic or already under depression treatment will be referred to mental health specialist care and excluded from the study. If the infant is born with congenital abnormalities or with other significant health problems, the mother-child dyad will be excluded.

Our data collection protocols that begin prenatally through 6 months postpartum will be synchronized with the main SHARE study (see Figure 1). After 6 months, SHARE ends and we continue the SHARE CHILD data collection. Interviews will be scheduled at 3, 6, 12, 24 and 36 postpartum month milestones for each mother-child dyad (see Table 1).

Table 1: Timeline of SHARE CHILD assessments

Breastfeeding		✓	✓	✓		
MSPSS	✓	✓	✓	✓	✓	✓
PHQ-9	✓	✓	✓			
WHO-DAS	✓	✓	✓			
Sociodemographic questions	✓			✓	✓	✓
BAYLEY				✓	✓	✓
HOME		✓	✓	✓	✓	✓
ASQ SE			✓	✓	✓	✓
Vineland			✓	✓	✓	✓
Height/Weight		✓	✓	✓	✓	✓
Maternal postnatal attachment		✓	✓			
Maternal efficacy		✓	✓			
Cohen PSS		✓	✓	✓	✓	✓
IPV	✓	✓		✓	✓	✓
CISR		✓	✓			✓
SDQ						✓
Risk game	✓			✓		
Stroop test	✓			✓		
Autonomy questions	✓			✓	✓	✓
A day in life		✓	✓			
Father involvement in child care	✓	✓	✓	✓	✓	✓

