2.2 Trial Design

THPP+ is a stratified cluster randomized controlled trial, with 40 village clusters allocated in a 1:1 ratio to the intervention and control arms within 11 strata defined by Union Councils. The unit of randomization is a village cluster (a population of 2400–3600 with 2-3 adjacent catchment areas of LHWs). Participants are recruited from the community. The reason for choosing a village cluster as the unit of randomization is to minimize contamination between trial participants, since the delivery of the intervention is community based.

Approximately 14 women who screened depressed on the PHQ-9 (≥ 10) in each of the 40 village clusters were invited to participate in the trial. Bachpan also contains an embedded cohort of non-depressed women. In each of the 40 village clusters, an equal number of women who screened non-depressed on the PHQ-9 (i.e., approximately 14 per cluster) were invited to participate.

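### For the continuous primary outcomes, the coded small-sample correction barely acts on the randomised contrast, and its standard error rests on unsupported joint-model assumptions; a depressed-only fit avoids this at low cost

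*SAP*

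**What the plan says.** The trial randomises village clusters, 20 per arm, within 11 union councils (SAP Sections 2.2 and 2.3). Besides the depressed women, in each cluster "an equal number of women who screened non-depressed on the PHQ-9 (i.e., approximately 14 per cluster) were invited to participate".

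SAP Section 3.1 analyses all women in one linear mixed model with three groups: depressed intervention, depressed control, and non-depressed from both arms combined. It states that "the between-within method will be used to apply small-sample corrections in the mixed effects framework". The code in Section 3.1.1 is "mixed sdqTotal i.arm3 i.ucCode || clusterCode:, reml dfmethod(repeated"), and X1 there "is a dummy variable for perinatally depressed intervention vs. control (1 if intervention; 0 if control").

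A separate random intercept for each group was considered, but "model convergence issues led us to revert to a single random intercept for cluster".

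On carryover, Protocol Section 3.1 says "we anticipate that non-depressed women in the intervention clusters will benefit from the trial". SAP Section 2.4 states for the non-depressed comparison that "we will have 80% power to detect a 1.7 or greater impact of the intervention on mean TD score". SAP Section 3 says "we will test for a differential effect by non-depressed in intervention vs. control as a supplemental analysis".

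**The concern.** Treatment is assigned to clusters, so information on the randomised contrast is limited by 40 clusters. In the three-group model, however, X1 is 1 for depressed women and 0 for non-depressed women in the same intervention cluster. The between-within method therefore treats it as a within-cluster covariate and uses a near-normal critical value. The promised correction hardly touches the contrast it is most needed for.

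The more serious consequence lies in the estimate and its standard error, because non-depressed women serve as an internal cluster control. That is valid only if:

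1. the cluster effect is fully shared by depressed and non-depressed women;
2. residual variance is the same in both;
3. the intervention has no effect in non-depressed women.

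The SAP does not justify the first two. Non-convergence of a richer model is not evidence that the simpler one is true. The only planning SD is 5.2, with none by depression group, and the planned residual checks name no comparison between those groups. The third runs against the protocol's stated expectation. At stake are the 5% level for the SDQ Total Difficulties (TD) and PHQ-9 mean contrasts, and the size of the estimated effect. Binary outcomes use GEE with robust standard errors and the Kauermann-Carroll correction, so the degrees-of-freedom and standard-error point does not apply to them.

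**Working it through.** **Inputs.** From SAP Section 2.4: 40 clusters, 11 councils, two-sided 5%, TD SD 5.2, ICC 0.04–0.08, target difference 3 points. I take m = 11 women per group per cluster (220 per arm), as in Protocol Section 3.1 and the SAP's equivalence calculation. Assumed, because the documents are silent: 9 councils of 4 clusters and 2 of 2; the ratio of non-depressed to depressed SD (q); the correlation between their cluster effects (r).

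**The plan's own power.** With 240 per arm, SE = 5.2 × √[2(1 + 11 × ICC)/240], which is 0.570 at ICC 0.04 and 0.651 at 0.08. Power = Φ(3/SE − 1.96) = 99.95% and 99.6%, consistent with the stated figure of more than 90%. This calculation uses depressed women only.

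**Degrees of freedom.** The joint model with 880 dyads has 13 fixed parameters, so 867 residual df: 40 − 11 = 29 between clusters and 838 within. With 960 dyads the within df is 918. X1 takes the within df, with critical value 1.963 (normal 1.960). Depressed-only, X1 is constant within cluster, the same method gives 40 − 11 − 1 = 28 df, and the critical value is 2.048. If the joint model is true, Satterthwaite df are 215–368 (critical value 1.966–1.971), so 28 is not the right reference for that model and the df alone matter little.

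**Standard error.** In this balanced layout the joint estimate is D_dep − w × D_non. Each D is the intervention-minus-control difference within that depression group, and w = m·ICC/(1 − ICC + m·ICC). Write a = ICC + (1 − ICC)/m. Then:

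- depressed-only variance = (2/20) × 5.2² × a
- true variance of the joint estimate = (2/20) × 5.2² × [a + w·ICC·(q² − 2rq)]

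Here q scales both variance components, and w is held at its planning value.

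At ICC 0.05, a = 0.05 + 0.95/11 = 0.1364, w = 0.55/1.50 = 0.367 and w·ICC = 0.0183.

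- Depressed-only: √(2.704 × 0.1364) = 0.607.
- Joint, all assumptions true (q = r = 1): √(2.704 × 0.1180) = 0.565.
- Joint, r = 0.5, q = 1: the added term is zero, so the true SE is again 0.607. The precision gain has gone, but the model still reports a smaller SE.
- Joint, q = 0.8, r = 1: the true SE is √[2.704 × (0.1364 − 0.96 × 0.0183)] = 0.567. The reported SE falls with the pooled variance, to about 0.565 × √0.82 = 0.512. The ratio is 1.108, and 2[1 − Φ(1.963/1.108)] is about 7.6%.

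**Simulated type I error.** REML fits, no effect in depressed women, 20,000 replicates per scenario, simulation error about ±0.3 to 0.5 percentage points, ranges over ICC 0.04–0.08:

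| Assumed truth | Coded model, t(838) |
|---|---|
| All assumptions hold | 5.4–5.6% |
| SD ratio 0.8 | 7.9–8.4% |
| Cluster-effect correlation 0.5 | 6.9–9.2% |
| Both | 10.2–12.3% |
| SD ratio 1.25 | 3.1–3.2% |

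The depressed-only fit with t(28) gave 4.4–5.0% in all of these.

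**Carryover.** At fixed ICC, w is 0.31 (ICC 0.04) to 0.49 (0.08), so that share of any benefit to non-depressed children is taken off the primary contrast. In REML fits, carryover also raises the estimated cluster variance, and hence w. The simulated shift is 0.35–0.51 points for an assumed 1-point benefit. For 1.7 points it is 0.68–0.93, which is 23–31% of the 3-point target. Power for 3 points is then 92.7–97.0% in the joint model and 99.2–99.8% depressed-only.

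**The case against.** The strongest reply is that the degrees of freedom are a side issue, and that the larger error rates come from SD ratios and correlations found nowhere in the documents. A village effect shared by both groups is a natural default. Fitting everything jointly has a stated purpose: every comparison comes from one model. Carryover to children is an open question in SAP Section 2.1, the 1.7 points is a detectable rather than an expected difference, and the resulting bias is conservative. Even then power stays above 90%.

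Much of this stands. The df effect is small if the model is right, the inputs are assumed, and the error can go either way. The protocol's expectation concerns non-depressed women and names neither an outcome nor a size.

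The cost of the alternative also grows for smaller effects. If the joint model is true, 2-point power falls from 93% to 83% at ICC 0.08. Power for 1.5 points falls from 77% to 69% at ICC 0.04 and from 73% to 59% at 0.08. The SAP is dated October 2019, after the stated end of the trial in August 2019, so a change of estimator needs a dated justification.

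The planned safeguards do not answer the point. The quantile regressions use the same three groups. The weighted and assessor-adjusted analyses relax none of the three assumptions. The supplemental carryover test leaves the primary estimate unchanged and, with 80% power at 1.7 points, could miss a smaller carryover that still shifts it.

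**Conclusion.** The concern holds for SDQ-TD and PHQ-9 mean score. The between-within correction is nearly inactive on the randomised contrast (838 or 918 df). More importantly, the nominal 5% level depends on assumptions that the plan neither justifies nor checks by depression group. Over the assumed departures the coded test rejects between 3.1% and 12.3% of the time. The direction in this trial is unknown because the documents give no SD or cluster correlation by depression group. If non-depressed children benefit, the estimate moves against the intervention by roughly a third to a half of that benefit. For PHQ-9 mean score the documents give no SD or target difference, so only the scale-free results carry over. This is a change that should be made because the alternative is simple and matches the population of the SAP's primary power calculation. The figures do not show that this trial's result is wrong.

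**What to change.** For SDQ-TD and PHQ-9 mean score, estimate depressed intervention versus depressed control in depressed women only, with union council and a cluster random intercept, keeping REML and the between-within method. The df are then 28. Keep the joint model for comparisons with non-depressed women, and report its version of the primary contrast as supportive.

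If the joint model must carry the primary contrast, split the non-depressed group by arm and let both residual variance and cluster effects differ by depression status. That version was not simulated and may meet the non-convergence the SAP reports. Partial repairs are not enough. At SD ratio 0.8, the coded SE with t(28) still rejects 6.7–7.1%. Four groups with t(28) reject 6.7–8.6% (cluster-effect correlation 1 or 0.5).

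The cost is one restriction in the code, a sentence in the SAP that dates and justifies the change, and a wider interval. At ICC 0.05 the half-width goes from 1.963 × 0.565 = 1.11 to 2.048 × 0.607 = 1.24 points (+12%), and the increase is 10% at ICC 0.04 and 20% at 0.08. Power for 3 points stays at 99% or more. For 2 points at ICC 0.05 it is about 89%, against 94% if the joint model is true.
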